Quantitative observational comparative effectiveness of quadratus lumborum block with liposomal bupivacaine (Exparel®) versus thoracic epidural analgesia in patients undergoing laparoscopic colectomy

NCT03827291

Document Date: 09/27/2022

Purpose of the Study

We believe that a quadratus lumborum block with liposomal bupivacaine(Exparel®) or a quadratus lumborum block with an admixture of bupivacaine will provide roughly equivalent analgesia and opioid use when compared with postoperative analgesia in a historical cohort that received thoracic epidural analgesia. We believe participants who receive the quadratus lumborum block will result in improved early mobilization, fewer complications such as block failure, urinary retention, and pruritis, and decreased overall pharmacy costs compared to the patients who received thoracic epidural analgesia.

Background & Significance

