Following the block, subjects will proceed to the operating room where they will undergo a standard general anesthetic with endotracheal intubation (desflurane or isoflurane in a mixture of air/oxygen). The dosing of intraoperative opioids will be left to the discretion of the attending anesthesiologist in the room.

In the Post-Anesthesia Care Unit (PACU) and on the postoperative floor, subjects will have access to oxycodone 5-15 mg PO q3h prn for rescue analgesia (the primary outcome measure). In the PACU, patients will also have access to intravenous hydromorphone if the oral opioid

provides inadequate relief. Finally, subjects may receive a standard multimodal analgesia regimen consisting of:

- Acetaminophen 975 mg PO q6h (beginning in preop holding)
- Gabapentin 600 mg PO once in holding, then 100 mg PO tid thereafter
- Ketorolac 15 mg IV prior to skin closure

While this standard regimen is expected, it may vary per clinical care team judgement and/or preference. Any alterations in this standard regimen will not be considered a protocol deviation.

Assessments

Patient assessments will be performed or recorded by a research assistant twice daily (unless otherwise specified). Assessments made after discharge will be recorded by subjects who will be provided with a diary to document the outcomes. Outcomes to be measured include:

Opioid consumption. Cumulative opioid consumption over 48 hours is the primary outcome measure. Data will be drawn from PACU records and from the nursing medication records on a twice-daily basis. Post discharge opioid use will be tracked in the take-home patient diary. The patient will be called at 7 days after surgery to collect.

NRS-11. The 11-point Numeric Rating Scale (0-10) will be used as a secondary outcome measure. Two measures will be taken with each assessment, one at rest and one with coughing. These will be conducted preoperatively, 30 minutes after arrival to PACU, and at time points 8 hrs., 24 hrs., 36 hrs. 48 hrs, 72 hrs, 96 hrs., 120 hrs., 144 hrs. and 168 hrs.

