Historical data of 30 patients that meet inclusion criteria and meet no exclusion criteria, will be collected and for the retrospective group. The anesthesia statisticians will evaluate the following data from the patient's electronic medical record if available, including but not limited to hospital notes, anesthesia notes, medical history, medications, pain service notes, and flowsheets from admission to discharge. Electronic medical records will be used to assess the following items to compare to the prospective cohort.

Opioid consumption. Cumulative opioid consumption at 24hours, 48 hours and 72 hours. 48 hours is the primary outcome measure. Data will be drawn from PACU records and from the nursing medication records.

NRS-11. The 11-point Numeric Rating Scale (0-10) will be used as a secondary outcome measure. These will be collected from the preoperative assessment record, 30 minutes after arrival to PACU, and at time points 8 hrs., 24 hrs., 36 hrs. 48 hrs. and 72 hrs.

Thoracic epidural success and adverse events. Evidence of epidural block success/failure (as described in the anesthesia record and in daily Inpatient Pain Service notes). This will be done at the time of pain assessment (30 minutes after arrival to PACU, and at time points 8 hr, 24 hr, 36 hr and, 48 hr and 72 hr). Subject data will be collected for potential adverse events related to the epidural including evidence of hypotension, urinary retention, inability to ambulate per physical therapy. (known possible side-effect of thoracic epidural approach).

Hospital length of stay. Measured both by raw length of stay and by time to achieving "discharge readiness", defined by the presence of 3 criteria: a pain score of 3 or less with ambulation, no opioids required in the preceding 6 hours, and the ability to perform self-care (go to the toilet, dress, and shower).

Incidence of opioid-related adverse events. Incidence of nausea, vomiting, ileus, constipation, orthostasis, pruritis, urinary retention, respiratory depression

Time to first mobilization. Measured from time of arrival in PACU (time zero)

Cost. Hospital costs including pharmacy-related costs, costs due to opioid-related adverse events, the cost associated with nursing interventions and drugs to treat opioid-related adverse events, and overall hospital admission costs will be calculated.

Selection of Subjects

Criteria for inclusion in Prospective cohort:

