We will use descriptive statistics (mean (SD) or frequency (%)) and group comparisons via Wilcoxon rank sum or fisher exact tests to measure differences between cohorts in opioid consumption, pain scores with rest and activity, and other secondary outcome measures.

Sample Size Justification

A difference in opioid consumption less than 20% would be considered non-inferior. Based on typical postoperative opioid consumption following laparoscopic colectomy (20mg +/- 5.2 mg), a total of 54 subjects (27 in each group) would be required to reject the null hypothesis that QL blockade is inferior in the first 48 hours with the study intervention, given an alpha of 0.05 and a power of 0.8. We plan on recruiting 45 subjects to account for dropout.

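### Pain scores are recorded in different ways in the two cohorts, so the between-cohort NRS comparison cannot separate pain from recording method, in either direction

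*Combined protocol and SAP*

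**What the plan says.** The Purpose of the Study section expects that QLB "will provide roughly equivalent analgesia and opioid use when compared with postoperative analgesia in a historical cohort" given TEA. NRS-11 pain is a secondary outcome in both cohorts.

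- **QLB (Assessments).** "Patient assessments will be performed or recorded by a research assistant twice daily (unless otherwise specified". For NRS, "Two measures will be taken with each assessment, one at rest and one with coughing". The nominal times are preoperative, 30 minutes after PACU arrival, then 8, 24, 36, 48 and 72 hours and daily on to 168 hours. After the patient leaves hospital the source changes: "Assessments made after discharge will be recorded by subjects who will be provided with a diary to document the outcomes". Pinprick testing is done at the same time as the pain assessment up to 72 hours.
- **TEA (historical data, NRS-11).** The 30 historical patients had surgery in the past year. Their data come from the electronic record as far as it holds them, including "flowsheets from admission to discharge". For NRS, "These will be collected from the preoperative assessment record, 30 minutes after arrival to PACU, and at time points 8 hrs", followed by 24, 36, 48 and 72 hours. No rest or cough condition is given.
- **Analysis (Data Analysis & Statistical Considerations).** Wilcoxon rank sum tests compare the cohorts on outcomes that include "pain scores with rest and activity". No NRS margin, adjustment or handling of missing or off-time scores is given.

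**The concern.** The hours listed for the two cohorts agree up to 72 hours, which makes the scores look comparable, but they arise differently. A QLB score belongs to a study assessment under a stated condition. A TEA score is whatever ward staff charted, at a time not set by this study and under a condition that the plan does not state. The plan does not say which charted score represents a given hour, how far from that hour it may lie, or what happens when there are several scores or none.

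All QLB scores come by one route and all TEA scores by another, so no analysis of these data can tell a difference in pain from a difference in recording. NRS is the direct measure of the analgesia half of the stated purpose, and opioid use is hard to interpret without a fair pain comparison beside it. A recording difference could create an apparent advantage or disadvantage for QLB, or hide a real one.

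**Working it through.** **1. The plan's own figure.** The only calculation in the plan is for 48-hour opioid use. With margin 0.20 × 20 = 4 mg, SD 5.2 mg, one-sided alpha 0.025 and power 0.80:

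n per group = 2 × (1.960 + 0.842)² × 5.2² / 4² ≈ 26.5, so 27 per group and 54 in total.

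This reproduces the stated 54. It concerns opioid use, and the plan gives no power or margin for NRS, so the present point changes no stated figure.

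**2. The two recording methods side by side.**

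| Feature | QLB | TEA |
|---|---|---|
| Source in hospital | Research assistant, taken or noted | Electronic record, where present |
| Source after discharge | Patient diary | None named |
| Condition | Rest and cough | Not stated |
| Nominal hours to 72 h | PACU 30 min, 8, 24, 36, 48, 72 | The same |
| Time window | Not stated | Not stated |
| Rule for choosing among charted scores | Not stated | Not stated, though all scores are charted ones |

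Source and condition differ completely by cohort. The missing window is common to both. It matters more in TEA, where charting was never scheduled to the study hours.

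**3. How large an effect recording alone could have.** The documents give no NRS mean, SD or recording shift, so everything here is an assumption except the test and the candidate group sizes. Model: true NRS is normal with mean 3 and SD 2 in both cohorts, rounded and limited to 0–10; half of the TEA scores are moved by a fixed amount; two-sided Wilcoxon at 0.05. The average shift is 0.5 × 1 = 0.5 point or 0.5 × 2 = 1 point. With no shift, each direction is significant in about 2.5% of studies.

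| QLB v TEA | Half of TEA scores moved by | False result | Share of studies |
|---|---|---|---|
| 45 v 30 | +1 | QLB better | about 17% |
| 45 v 30 | +2 | QLB better | about 49% |
| 45 v 30 | −1 | QLB worse | about 15% |
| 45 v 30 | −2 | QLB worse | about 46% |
| 27 v 27 | +1 | QLB better | about 13% |
| 27 v 27 | +2 | QLB better | about 39% |

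These carry simulation error of a point or two. The share affected matters as well. At 45 v 30 with upward shifts of 1 and 2 points, about 7% and 15% of studies are falsely favourable to QLB if a quarter of TEA scores are affected, and about 34% and 85% if three quarters are.

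**4. The converse.** In a second assumed model (TEA mean 4, SD 2.0 to 2.5, 27 v 27), QLB pain is truly 1 point worse. The test detects this in 29–42% of studies. If all charted TEA scores are 1 point too high, detection falls to about 5%, the false-positive level of the test.

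**The case against.** The strongest reply is that the contrast can be drawn too sharply. Several parts of it stand.

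- The QLB text allows the assistant to record scores as well as perform assessments, so some may be transcribed. Paired rest and cough scores alongside pinprick testing point to bedside assessment, but do not prove it for every score. Scores after discharge are diary entries, and these can include 72 hours for a patient already at home.
- QLB has no stated window either, so the missing window is not a defect of the TEA cohort alone.
- A reader might infer that the comparison favours QLB, because charted scores may cluster around requests for rescue. The documents do not say this. They name daily pain service notes and flowsheets among the TEA sources, so some scores may come from rounds. Cough scores are specified only for QLB and could push the other way. The direction is unknown, and bias at every time point is not established: the comparison could be biased.
- Charting in both cohorts could itself differ around rescue requests. If 50% of QLB and 25% of TEA charted scores were raised by 1 or 2 points (assumed shares), QLB would look falsely worse in about 7% or 16% of studies. A common source removes the difference in recorder, but not this.
- NRS is secondary and has no formal equivalence test. The size of 45 for QLB is one reading, since Sample Size Justification does not say whether 45 is a total.

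None of this removes the confounding of recording method with cohort.

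**Conclusion.** The point holds as a weakness of the secondary pain comparison that is worth correcting. That source and condition differ by cohort, with no rule for selecting a charted score, follows from the text and needs no assumption. The size does rest on assumptions: a recording shift of 1 to 2 points in half of the TEA scores would give a false difference in about 13% to 49% of studies across the group sizes and directions tabulated, against a nominal 2.5%. Neither the size nor the sign of any real shift can be derived from the documents.

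A reader might extend this to the primary outcome. The documents do not support that for in-hospital data: 48-hour opioid use is drawn from PACU and nursing medication records in both cohorts. The exception is diary data after discharge, which exist for QLB only.

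**What to change.** For the between-cohort pain comparison, use staff-charted in-hospital NRS from the electronic record in both cohorts, under one rule fixed before the scores are abstracted:

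- At PACU 30 minutes and at 8, 24, 36, 48 and 72 hours, take the charted score nearest in time within a common window, narrow enough that no score serves two time points. Count the value as missing if the window is empty.
- As a sensitivity analysis, compare each patient's time-weighted mean of charted scores over 0–24, 24–48 and 48–72 hours.
- Report the number of charted scores and of missing scores by cohort and window, including loss after discharge.
- Keep the assistant's rest and cough scores and the diary scores as QLB-only description, and amend the analysis section's reference to rest and activity accordingly.

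The cost is record abstraction for the QLB patients and a short addition to the analysis section. It assumes that QLB patients have routinely charted scores, which is reasonable for inpatients at the same centre but is not stated. The cough-specific comparison between cohorts is lost, though the plan never specified a cough score for TEA. Any difference between cohorts in charting around rescue requests would remain and should be reported as a limitation.

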Laparoscopic colectomy is a surgical procedure that is primarily performed for resection of a GI malignancy. While most of the procedure is performed via laparoscopic ports in the anterior abdominal wall, the resected specimen is typically delivered through a small lower abdominal laparotomy, which results in a moderately severe burden of pain for these patients. Enhanced recovery after surgery (ERAS) protocols are aimed at improved return to function with minimal disruption in the functional capacity, and have been shown to reduce hospital length of stay, complications, and costs. One standard therapeutic component of the ERAS program at Duke for colorectal surgery is thoracic epidural analgesia (TEA), which is typically maintained for 2 days postoperatively. While TEA usually provides high-quality analgesia of the abdomen, drawbacks include technical difficulties with insertion, patchy or non-functioning block, pruritis and/or urinary retention due to epidural opioids, impairment of mobility due to leg weakness or the presence of a pump apparatus on an IV pole, and most importantly, associated hypotension which often results in the epidural local anesthetic infusion being discontinued. Alternatives to TEA include infiltrative blocks of the wall of the abdomen. The quadratus lumborum block (QLB) is a novel, ultrasound-guided infiltration technique whereby local anesthetic is deposited in the fascial plane between the quadratus lumborum and psoas major muscles at the level of L3-4.(1) Performed bilaterally, the QLB has been shown to provide a dermatomal block of the entire anterior abdominal wall. This may be the principal advantage of QLB over transversus abdominis plane (TAP) block, which is often patchy and restricted to a smaller area of the abdominal wall. In our institution, QLB is replacing TAP blockade for many abdominal procedures that have both upper and lower incisions or port sites. The QLB appears (both in the scant literature to date and in our institutional experience) to be reliable and technically simpler to perform than TAP blocks, as the needle is not moved once the fascial plane is breached. We wish to compare the effectiveness of QL blocks for postoperative analgesia in this population with a historical cohort that received thoracic epidural analgesia. Based on our experience, we believe that infiltrating this space with an admixture of bupivacaine and liposomal bupivacaine will result in excellent pain relief for an extended duration of time. Liposomal bupivacaine (Exparel®) is a slow-release, long-acting form of bupivacaine that has been shown to provide extended duration of analgesia and opioid sparing

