Block success and adverse events. Presence of demonstrable sensory block over 4 points on the abdomen (one in each of the 4 quadrants), as tested by response to pinprick. Subjects will be asked to report whether the stimulus feels “sharp” or “dull”, indicating block failure and success respectively. This will be done at the time of pain assessment (30 minutes after arrival to PACU, and at time points 8 hrs., 24 hrs., 36 hrs. and 48 hrs. and 72 hrs.). Subjects will be evaluated for potential adverse events related to the block including evidence of hematoma, infection, unexpected sensory or motor deficit, local anesthetic systemic toxicity, as well as transient weakness of the hip flexor muscles (a known possible side-effect of QL block).

Satisfaction with postoperative pain control. Overall subject satisfaction with pain control will be recorded on postoperative day 0 and 1 (11-point scale: 10=highly satisfied, 0=completely unsatisfied)

Hospital length of stay. Measured both by raw length of stay and by time to achieving “discharge readiness”, defined by the presence of 3 criteria: a pain score of 3 or less with ambulation, no opioids required in the preceding 6 hours, and the ability to perform self-care (go to the toilet, dress, and shower).

Incidence of opioid-related adverse events. Incidence of nausea, vomiting, ileus, constipation, orthostasis, pruritis, urinary retention, respiratory depression

Time to first mobilization. Measured from time of arrival in PACU (time zero)

Cost. Hospital costs including pharmacy-related costs, costs due to opioid-related adverse events, the cost associated with nursing interventions and drugs to treat opioid-related adverse events, and overall hospital admission costs will be calculated.

Sleep Quality. Two measures will be taken for sleep quality assessment. How much did pain interfere with falling asleep (0= no interference, 10= completely interferes). How much did pain interfere with staying asleep (0= no interference, 10= completely interferes). Measures will be taken once daily from POD 1 to POD 7 (approximately 168hrs. after surgery). If the subject is sleeping at the time assessment collection is due, the subject will not be disturbed to collect the assessments, and this will not be considered a protocol deviation.

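### Block failure is compared between cohorts but ascertained by pinprick for QLB and by note wording, with no criterion, for TEA; the condition of the TEA pain scores is also unstated

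*Combined protocol and SAP*

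**What the plan says.** The Purpose of the Study section lists block failure among the complications expected to be less common with QLB than with TEA. The paragraph that introduces the historical data says: "Electronic medical records will be used to assess the following items to compare to the prospective cohort". Epidural success or failure is on the list that follows. Data Analysis & Statistical Considerations then applies Wilcoxon rank sum or Fisher exact tests between cohorts to opioid use, pain at rest and with activity, and the remaining secondary measures. It does not name block failure individually.

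For the QLB cohort (Assessments, Block success and adverse events), the measure is "Presence of demonstrable sensory block over 4 points on the abdomen (one in each of the 4 quadrants), as tested by response to pinprick". Sharp and dull answers are taken as "indicating block failure and success respectively".

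For the TEA cohort (Thoracic epidural success and adverse events), the measure is "Evidence of epidural block success/failure (as described in the anesthesia record and in daily Inpatient Pain Service notes". The data come from the "electronic medical record if available". Readings are taken 30 minutes after arrival in the PACU and "at time points 8 hr, 24 hr, 36 hr and, 48 hr and 72 hr". The QLB cohort has the same times.

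Background & Significance describes "thoracic epidural analgesia (TEA), which is typically maintained for 2 days postoperatively", and names among the drawbacks "associated hypotension which often results in the epidural local anesthetic infusion being discontinued".

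For pain, the prospective NRS-11 item specifies scores at rest and on coughing. The retrospective NRS-11 item states no condition.

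**The concern.** A bedside sensory examination and a clinician's description in a note are different instruments. They can disagree about the same patient: a small unblocked area may be found on pinprick and never written down, and a note may record a failure for reasons that pinprick would not detect. If one instrument is used in one cohort and the other in the other, an observed difference in failure cannot be attributed to the technique alone.

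Two gaps add to this. Neither cohort has a rule that turns six readings into one result per patient. For TEA, nothing says how to classify a catheter already removed, an infusion already stopped, or a time at which nothing was written.

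At stake is the secondary claim that QLB has fewer block failures, and the comparison of pain at rest and with activity.

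**Working it through.** The plan gives no figure for block failure or for pain scores, so there is none to reproduce. The stated sample size concerns 48 h opioid consumption and does not depend on this point. The check is a comparison of the two cohorts' definitions.

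| Element | QLB cohort | TEA cohort |
|---|---|---|
| Method | Pinprick at four points | Anesthesia record and daily pain-service notes |
| Criterion at one time | Sharp or dull at each point; can be read as requiring all four dull | None stated |
| Times | 30 min after PACU arrival, then 8, 24, 36, 48, 72 h | Same six times |
| Rule across times | None | None |
| Ended or stopped technique | Single injection on each side, so no catheter to remove | No coding given |
| Undocumented reading | No coding given | No coding given; source used only if available |
| Pain condition | Rest and cough | Not stated |

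**Step 1: is a comparison intended?** Yes. The purpose section predicts a difference in block failure, the historical items are collected to be compared, and secondary outcomes are tested between cohorts. That block failure would get a Fisher test is an inference from the general wording of the analysis section.

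**Step 2: the 72 h reading.** TEA typically lasts 2 days, and 2 × 24 h = 48 h. The 72 h reading is therefore 72 − 48 = 24 h after the usual end. QLB is also read at 72 h; what is specific to TEA is that the technique being judged has usually been withdrawn by then.

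**Step 3: which way could the result move?** The inputs here are assumptions, chosen only to show that the sign is open. Suppose true failure is 10% in both cohorts, and observed failure = true rate × sensitivity + (1 − true rate) × (1 − specificity).

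- Pinprick with sensitivity and specificity both 0.95: 0.10 × 0.95 + 0.90 × 0.05 = 14.0%.
- Notes that miss failures (sensitivity 0.60, specificity 1.00): 0.10 × 0.60 + 0.90 × 0 = 6.0%. TEA minus QLB = −8.0 points.
- Notes that over-record failure, for example if ended epidurals are coded as failed (sensitivity 0.95, specificity 0.70): 0.10 × 0.95 + 0.90 × 0.30 = 36.5%. TEA minus QLB = +22.5 points.

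With no true difference, the apparent one can favor either technique.

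**Step 4: does the missing rule across times matter?** Assume 10% fail at each time. If the same patients fail every time, both a failed-at-any-time rule and a failed-at-all-times rule give 10%. If the times were independent, which is an extreme case for repeated tests in one patient, the first gives 1 − 0.9^6 = 46.9% and the second 0.1^6, about 0%. A rule can thus raise or lower the rate. The documents propose neither rule, and the gap is the same in both cohorts.

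**Step 5: pain.** The analysis compares pain at rest and with activity. Even if activity means cough, the retrospective item does not say that cough scores, or scores labeled as taken at rest, will be available. Pain with ambulation appears for both cohorts only as a threshold within discharge readiness, not as part of the NRS series.

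**The case against.** A historical cohort cannot be examined by pinprick after the fact. The plan declares its mixed prospective and retrospective design openly and limits itself to what the record holds. Because the six times match, cohorts can be compared time by time without a patient-level rule, and a large difference in the PACU or at 8 h would still be informative. The analysis section does not name block failure, and the primary outcome is untouched.

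Much of this stands. Time-by-time comparison does remove the need for a combining rule, and a large early difference would carry some weight. It does not remove the difference in instruments at each time, and it does not settle how an ended epidural is coded at 72 h. That pinprick cannot be obtained in retrospect is a reason to base the comparison on what both cohorts can supply.

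Some stronger readings are tempting but not supported:

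- A reader might infer that only QLB lacks a rule across times, or that only TEA is read to 72 h. Both features are shared.
- A reader might infer from the background that stopped infusions are frequent. The text says that hypotension, when it occurs, often leads to discontinuation; it gives no overall frequency.
- A reader might infer that the TEA pain scores have no matching condition. The plan is silent, and the flowsheets may record one.
- A reader might see a further fault in the differing adverse-event lists. The QLB list is introduced as non-exhaustive, urinary retention is on the opioid-related list in both cohorts, and the purpose section makes no claim about hypotension.

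**Conclusion.** The concern holds for the ascertainment of block failure. As planned, a between-cohort test would combine the effect of the technique with the effect of using pinprick in one cohort and uncriterioned note wording in the other, and the TEA side has no coding for ended or stopped epidurals. The net direction is unknown. A reader might take the percentages in the working as estimates of bias. They are not: the documents give no failure rates, no accuracy for either method and no rate of catheter removal, so no magnitude can be stated.

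For pain, the supportable conclusion is narrower: the condition under which TEA scores were taken is unstated, so the planned rest and activity comparison is not defined for that cohort.

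Only secondary outcomes are affected. In-hospital data for the 48 h opioid primary are named from PACU and nursing medication records in both cohorts. This should be corrected before the between-cohort analysis is run.

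**What to change.** For the between-cohort test, write one explicit block-failure definition that fits both a single injection and an infusion, and abstract it the same way from record types that exist for both cohorts. Limit it to times up to 48 h. State in advance how ended or stopped epidurals are coded for analysis, and keep not documented as its own category rather than folding it into success or failure. Report pinprick descriptively for QLB only.

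If no common definition is workable, report block success within each cohort and drop the between-cohort block-failure claim.

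Compare pain using routinely charted NRS from the same record source in both cohorts, and report cough scores descriptively for QLB.

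The cost is some extra chart abstraction, including for QLB patients, and a failure measure less sensitive than examination. Charting intensity may still differ: TEA patients have daily pain-service notes, while QLB patients are assessed twice daily by a research assistant. That remaining difference should be stated as a limitation. The primary comparison does not change.

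### Hypotension is a specified outcome in the epidural cohort only, so any between-cohort comparison of hypotension would be biased toward the QL block

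*Combined protocol and SAP*

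**What the plan says.** Background & Significance lists several drawbacks of TEA and gives one of them special weight: "most importantly, associated hypotension which often results in the epidural local anesthetic infusion being discontinued".

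For the historical cohort, the paragraph on thoracic epidural success and adverse events says: "Subject data will be collected for potential adverse events related to the epidural including evidence of hypotension, urinary retention, inability to ambulate per physical therapy". The lead-in to the historical items gives their purpose: "Electronic medical records will be used to assess the following items to compare to the prospective cohort". The stated sources are notes and flowsheets from admission to discharge, where available.

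For the prospective cohort, the paragraph on block success and adverse events under Assessments names "potential adverse events related to the block including evidence of hematoma, infection, unexpected sensory or motor deficit, local anesthetic systemic toxicity", and also transient hip flexor weakness. Hypotension is not among them. The opioid-related list is identical in both cohorts: "Incidence of nausea, vomiting, ileus, constipation, orthostasis, pruritis, urinary retention, respiratory depression". It has orthostasis but not hypotension.

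Purpose of the Study predicts "fewer complications such as block failure, urinary retention, and pruritis" with QLB. Data Analysis & Statistical Considerations plans "group comparisons via Wilcoxon rank sum or fisher exact tests to measure differences between cohorts" for opioid use, pain scores and the other secondary outcomes.

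**The concern.** A rate can be compared between cohorts only if the event is looked for in both. Here it is looked for in the TEA charts. In the QLB cohort it would be recorded only if someone happened to note it. QLB patients also have general anesthesia, abdominal surgery and access to opioids, so their true count cannot be taken as zero. No threshold or time window for hypotension is given for either cohort.

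Two outcomes are possible if the plan is followed as written. A TEA count may be tested against zero or against incidental QLB reports, which can produce a significant advantage for QLB when the true rates are equal. Or the comparison is left out, and the study says nothing comparative about the drawback of TEA that its own background ranks first.

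**Working it through.** **Step 1. Set the item lists side by side.**

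| Item | QLB cohort | TEA cohort |
|---|---|---|
| Hypotension | not named | named |
| Inability to ambulate per physical therapy | not named | named |
| Hematoma, infection, sensory or motor deficit, systemic toxicity, hip flexor weakness | named | not named |
| Urinary retention | named (opioid-related list) | named (both lists) |
| Orthostasis and the other opioid-related events | named | named |
| How collected | research assistant, twice daily unless otherwise specified | chart abstraction, where available |

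Blood pressure in QLB patients appears in Design & Procedures only as monitoring during block placement, not as an outcome. The historical section lists hypotension and orthostasis separately, so the plan itself treats them as two items. Orthostasis is a postural finding and does not capture low pressure at rest.

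**Step 2. Group sizes.** The historical section gives 30 TEA patients. Sample Size Justification requires 27 per group. That figure reproduces: the margin is 20% of 20 mg = 4 mg, the SD is 5.2 mg, one-sided alpha is 0.025 and power is 0.80, so n = 2 × (1.960 + 0.842)² × 5.2² / 4² = 26.5, rounded up to 27 per group and 54 in total. The plan does not state sidedness; one-sided 0.05 would give 21 per group. The present point does not depend on this calculation except for the group size.

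The same section plans to recruit 45 subjects without saying to which cohort they belong. I show 45 QLB patients as a second case, on the assumption that all 45 are prospective.

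**Step 3. Smallest significant TEA count when QLB is scored as zero (two-sided Fisher, 0.05).**

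- 27 QLB patients: 5/30 v 0/27 gives p = 0.053; 6/30 v 0/27 gives p = 0.0245. The critical count is 6.
- 45 QLB patients: 3/30 v 0/45 gives p = 0.060; 4/30 v 0/45 gives p = 0.0225. The critical count is 4.

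**Step 4. Chance of a false result favoring QLB.** The documents give no hypotension rate, so a true rate r, equal in both cohorts, is assumed. With QLB scored as zero, the chance is P(X ≥ critical count) for X ~ Binomial(30, r). At r = 0.20:

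- 27 QLB patients: 1 − P(X ≤ 5) = 1 − 0.428 = 0.572
- 45 QLB patients: 1 − P(X ≤ 3) = 1 − 0.123 = 0.877

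If a fraction c of QLB events is recorded, the QLB count is Binomial(n, c·r). The joint probabilities are then summed over all tables with Fisher p < 0.05 and a higher TEA proportion.

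| True rate in both cohorts | QLB events recorded | 27 QLB v 30 TEA | 45 QLB v 30 TEA |
|---|---|---|---|
| 5% | none | 0.3% | 6.1% |
| 10% | none | 7% | 35% |
| 20% | none | 57% | 88% |
| 30% | none | 92% | 99% |
| 10% | half | 2.2% | 8.5% |
| 20% | half | 12% | 17% |
| 30% | half | 23% | 29% |
| 20% | 80% | 3.8% | 4.7% |
| 20% | all | 1.7% | 1.8% |

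With equal ascertainment the figure stays below 2% at each of these rates.

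**The case against.** The strongest case against has four parts.

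- **The mismatch runs both ways.** Five kinds of event are named for QLB only, and QLB patients are actively assessed while TEA data depend on what was charted. Both features could raise the QLB complication count relative to TEA. This stands. A reader might infer that the complication comparison as a whole tilts toward QLB; the documents do not support that, and the direction is shown for hypotension alone.
- **No hypotension test is expressly planned.** The complication hypothesis names block failure, urinary retention and pruritus, and no pooled complication endpoint is defined. The two lists could be read as technique-specific safety lists. This stands in part: the harm arises only if hypotension is compared or enters a complication total. But the hypothesis gives only examples, and the historical lead-in states comparison as the purpose of every item under it.
- **Hypotension could still be recorded in QLB patients.** The QLB list is open-ended, and the study already draws on PACU and nursing medication records for these patients. This also stands. A reader might infer that hypotension can be counted in one cohort only; the accurate statement is that it is specified in one cohort only. An open list permits a note but requires none.
- **The large percentages are a worst case.** They treat uncollected events as zero and assume equal true rates, although the background presents hypotension as an effect of TEA. This stands, and Step 4 therefore shows partial capture too. A true excess with TEA is plausible, but it can be demonstrated only by measuring both cohorts.

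**Conclusion.** The point holds for hypotension. It is a specified item in the TEA cohort, collected for comparison, and not a specified item in the QLB cohort, so a between-cohort comparison would be biased toward QLB. No net direction across all complications is shown.

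The size depends on assumptions that the documents cannot settle. At an assumed true rate of 20% in both cohorts and 30 TEA patients, the chance of a false significant result favoring QLB runs from about 4% to 5% when 80% of QLB events are recorded, through 12% (27 QLB) or 17% (45 QLB) at half capture, to 57% or 88% in the worst case. At a 5% rate with 27 QLB patients it is negligible even with no capture. The 45-patient figures rest on a further assumption about whom the recruitment target covers.

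The primary outcome, 48-hour opioid consumption, is not affected. This is a secondary safety item that should be corrected because the plan itself gives it such weight.

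**What to change.** Add hypotension to the QLB outcomes. In both cohorts, abstract it from the same sources: charted blood pressures and recorded treatment of hypotension in PACU and nursing flowsheets. Fix one outcome definition, one time window (for example PACU arrival to 48 hours, or discharge if earlier) and one abstraction form before the data are reviewed, and compare incidence per patient. Do not set TEA hypotension against QLB orthostasis.

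Apply one common adverse-event list to both cohorts where the chart allows, including the items now named for QLB only. If this is not done, report cohort-specific events descriptively and make no between-cohort claim about them.

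The cost is a little more chart abstraction, with no added visit, procedure or patient. The apparent advantage of QLB on hypotension may shrink. Charting frequency may still differ between epidural and non-epidural patients, and the report should state that limitation.
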